13 SAFETY

The site investigator of each study centre is responsible for monitoring the safety of subjects for that study centre.

Immediate medical attention should be provided to resolve any SAE which occurs during the study. All AEs and SAEs occurring after any administration of the study drug will be followed until resolution or are clearly determined to be due to the patient's stable or chronic condition or intercurrent illness.

13.1 Definitions

Adverse event

An adverse event (AE) is any untoward medical occurrence in a patient administered a pharmaceutical product and which does not necessarily have a causal relationship with this treatment.

An AE can therefore be any unfavourable and unintended sign (including an abnormal laboratory finding, for example), symptom, or disease temporally associated with the use of a medicinal (investigational) product, whether or not considered related to the medicinal (investigational) product.

All AEs, including observed or volunteered problems, complaints, or symptoms are to be recorded. Each AE is to be evaluated for duration, intensity and causal relationship with the study medication or other factors.

The most anticipated AEs associated with Aspirin use are gastrointestinal related, majority of which are minor and resolved without any medical intervention. In rare cases, more serious effects, such as bleeding can be occurred in patient with long-term Aspirin use. Even less, haemorrhagic stroke can occur.

Adjuvant chemotherapy related toxicities can occur, however they are not regarded as AE for this study.

Serious adverse event

A serious adverse event (SAE) is any untoward medical occurrence that:

- Results in death
- Is life-threatening
- Requires inpatient hospitalisation or prolongation of existing hospitalisation
- Results in persistent or significant disability/incapacity, or
- Is a congenital anomaly/birth defect

A medical event that may not be immediately life-threatening or result in death or hospitalisation but may jeopardise the patient or may require intervention to prevent a serious outcome may also be considered serious (e.g. intensive treatment in an emergency room or at home for allergic bronchospasm; blood dyscrasias or convulsions that do not result in hospitalisation; or development of drug dependency or drug abuse). Medical and scientific judgement must be exercised when classifying events as serious.

When SAE occurs, the subject will be reassessed and investigator will consider whether to continue or discontinue study medication.

Unexpected adverse drug reaction (UADR)

An UADR is defined as an adverse reaction, the nature or severity of which is not consistent with the applicable product information (e.g. investigator's brochure for an unapproved investigational product or package insert/summary of product characteristics for an approved product).

13.2 Reporting of Adverse Event

All AEs will be recorded on the AE form in the subject's case report form.

The site investigator (international site or local site) is responsible to report **all SAEs** with de-identified relevant reports **within 1 working day** of the knowledge of the event to all of the following:

- Attention to monitor or project coordinator
- Investigational Product Manufacturer (Bayer AG)

The site investigator is also responsible to report all SAEs to relevant ethics committee or institutional review board within the required timeline. All SAEs will be followed up until resolution with updated information reported whenever available to the relevant parties as per initial reporting procedure.

The study monitor/project coordinator will notify the study co-chair and study project manager with the submitted SAE report by the site. The study co-chair will review the SAE report and recommendations will be sent to the site investigators if any.

The study co-chair is responsible to ensure any serious and unexpected adverse drug reaction occurring in the study is notified to all participant sites for reporting to ethics committee(s) or institutional review board(s) of all study centres and regulatory body (ies) of the country (ies) where the study is conducted by using the CIOMS Form. Fatal or life-threatening unexpected adverse drug reaction must be notified immediately but no later than 7 calendar days after the first knowledge by the study co-chair, followed by a complete report within 8 additional calendar days. All other serious, unexpected adverse drug reactions that are not fatal or life threatening must be reported within 15 calendar days after first knowledge by the study co-chair. The CIOMS Form will be sent to Bayer AG for review before distributing to all participating sites.

After discontinuation of treatment, patients should be carefully monitored for the occurrence of new adverse events up to 30 calendar days (follow-up period) after the administration of the last dose of aspirin. Adverse events are to be assessed in terms of their seriousness, severity, and relationship to the study drug. Only serious adverse (SAEs) should be reported to Bayer AG.

AEs and SAEs will be recorded from the time of entry into the study until 30 days after the full completion of study treatment, or in instances of early drug termination 30 days after the final cessation of study drug.

13.3 Reporting of Death

The site investigator is responsible for reporting all deaths that happen after 30 calendar days of study drug discontinuation until study completion date within 14 days of first knowledge by the Site Investigator to the study monitor/project coordinator. Date of death, cause and related information - will be documented as specified by the Trial Management Group.

The study monitor/project coordinator will notify the study co-chair and study project manager with the submitted report by the site. The report will be reviewed by the study co-chair and recommendations will be sent to the site investigators if any.

14 SUB-STUDIES (For Singapore and Selected Sites Only)

14.1 Blood Samples

Only patients who consent for research bloods will have 30 mls of blood collected at the time of consent and at 6 and 12 months after randomisation. The blood will be spun down and the buffy coat and serum aliquoted and stored separately in liquid nitrogen and at minus 80 degrees respectively. Each sample will be coded by a study number with no patient identifiers.

14.1 Biomarkers, protein, lipid and leukocyte profiling

Biomarkers will be investigated for possible association with clinical outcomes (disease free survival, overall survival) and for the effects of the study medication. Protein biomarkers related to inflammation and adaptive immunity will be profiled using standardised high throughput techniques. Lipid biomarkers derived from the metabolism of fatty acids which may be affected by COX activity will be profiled using HPLC. Leukocyte subsets and their function will be characterised by flow cytometry.

14.2 Germline DNA

DNA will be extracted using standardised methods and stored for subsequent genotyping. Genotyping for polymorphisms in drug targets and metabolising enzymes of relevance to aspirin and susceptibility to or prognosis of colon cancer will be performed using previously described techniques. Known functional SNPs of *COX 1 and COX2*, Prostaglandin synthases, and *CYP2C9* will be characterized using high throughput sequencing techniques.

14.3 Stool Samples

Stool Samples will be collected once at the following time points: Before initiation of study drug or any time points after initiation of study drug. Stool will be collected in a sterile specimen container and approximately one gram will be sealed in cryovials and snap frozen in liquid nitrogen before storage at -80 degrees Celsius. Stools will be analyzed in batches for *Streptococcus bovis* and other colonic flora. Association analysis will be made between colonic flora and clinical outcomes.

14.4 Urine Samples.

Urine specimens will be collected at the time of entry into the study before initiation of aspirin, and at 6 and 12 months after randomisation. Urine will be collected in a sterile specimen container and aliquot into vials to be stored at -80 degrees. Urine will be analysed for prostaglandin metabolites levels that will be correlated with aspirin treatment and outcomes.

14.5 Archival tumour specimens

In consenting patients, where samples are available, archived paraffin embedded tumour tissues will be retrieved, annotated, and stored till the end of the study where they will then be reviewed for immunohistochemical COX 1/2 staining and graded according to intensity of staining. Correlation will be made between intensity of Cox 1/2 staining and aspirin benefit. Archived tumour tissue will be stained for leukocyte subsets and correlation made with COX staining, survival and aspirin benefit.

DNA will also be extracted from archival paraffin tumour samples and tumour PIK3CA mutational status will also be assessed and analysed according to Aspirin exposure.

15 DIRECT ACCESS TO SOURCE DATA

The investigator will permit study related monitoring, audits, MCRC and/or EC review and regulatory inspection(s), providing direct access to the source data/ documents.

16 QUALITY CONTROL AND QUALITY ASSURANCE

This study will be monitored by delegated monitors according to its standard operating procedures. All protocol amendments will be in collaboration with SCRI. All administrative changes and regulatory reports/ approvals will be reported to Trial Management Group. The Investigator at each study centre must ensure that the study is conducted in compliance to the approved study protocol at the respective centre.

17 ETHICAL CONSIDERATIONS

This study shall be conducted in accordance to the principles of ICH E6 and any relevant research requirements. The study protocol should be reviewed and approved by the institutional review board or ethics committee of each participating centre. This will be the responsibility of each participating investigator.

The patient's written informed consent to participate in the study should be obtained after a full explanation has been given of the treatment options, including the conventional and generally accepted methods of treatment and the manner of treatment allocation.

The right of the patient to refuse to participate without giving reasons must be respected. After the patient has entered the study, the clinician remains free to give alternative treatment to that specified in the protocol at any stage if he/she feels it to be in the patient's best interest. However, the patient will need to remain within the study for the purpose of follow-up and data analysis. Similarly, the patient remains free to withdraw at any time from protocol treatment without giving reasons and without prejudicing his/her further treatment.

Records identifying the patient will be kept confidential and will not be made publicly available. If the results of the study are presented or published, the patient's identity will be kept confidential. The monitor(s), auditor(s), the Ethic Committee/ Institutional Review Board, and the regulatory authority (ies) will be granted direct access to patient's original medical records for verification of clinical study procedures and/or data, without violating the patient confidentiality.

18 INSURANCE

Study related injury would be determined by the institution insurance policy of the centre.

19 PUBLICATION POLICY

The results from all participating centres will be analysed together and published as soon as possible. Individual clinicians must not publish data concerning their patients that are directly relevant to

questions posed by the study until the main study report is published. The study results will be published under the ASCOLT Study Group.

20 STUDY ORGANISATION

The day-to-day running of the ASCOLT study will be managed by the Trial Management group. However, the ASCOLT study will also be subject to review by the Trial Steering Committee, Data Safety Monitoring Committee and Trial Management Group. Each committee will comprise of a mixture of independent members, study principal investigators, representatives from Trial Management Group, project manager and statisticians. For a full breakdown of committee members, please refer to the beginning of the protocol.

Data Monitoring Committee

The Data Monitoring Committee (DMC) is an independent group of individuals who are appropriately qualified and experienced in clinical trials. These individuals will be responsible for overseeing the safety aspects of the trial. The detailed plan of DMC review is stated under protocol 12.3 interim analysis. The DMC members will be confirmed within one year of study kick-off.

Trial Steering Committee

The Trial Steering Committee (TSC) is responsible for assessing the trial's overall progress, sample use, sanctioning or proposing any protocol changes, reviewing and approve publication data and abstracts, review trial endpoints, efficacy data, site performance, approving any proposals made by the TMG to change the design of the trial. This committee will receive and act upon reports from both the Trial Management Group and the DMC.

Trial Management Group

The Trial Management Group (TMG) is responsible for acting on the advice and recommendations of the DMC, and TSC. They will be responsible for acting on the advice and proposals given by the TSC and DMC committees, putting procedures in place, planning the course of action for the trial, problem solving any major issues and overall trial coordination.

APPENDIX 1 – TNM AND DUKES STAGING FOR COLORECTAL CANCER

TNM and Dukes Staging for Colorectal Cancer

Primary Tumour (T)

Tx	Primary tumour cannot be assessed
T0	No evidence of primary tumour
Tis	Carcinoma in situ: intraepithelial or invasion of lamina propria*
T1	Tumour invades submucosa
T2	Tumour invades muscularis propria
T3	Tumour invades through the muscularis propria into the subserosa, or into non-peritonealized pericolic or perirectal tissues
T4	Tumour directly invades other organs or structures, and/or perforates visceral peritoneum** , ***

* Note: Tis includes cancer cells confined within the glandular basement membrane (intraepithelial) or lamina propria (intramucosal) with no extension through the muscularis mucosae into the submucosa.

** Note : Direct invasion in the T4 includes invasion of other segments of the colorectum by way of the serosa; for example, invasion of the sigmoid colon by a carcinoma of the cecum.

*** Tumour that is adherent to other organs or structures, macroscopically, is classified T4. However, if no tumour is present in the adhesion, microscopically, the classification should be pT3. The V and L substaging should be used to identify the presence or absence of vascular or lymphatic invasion.

Regional Lymph Nodes (N)

Nx	Regional lymph nodes cannot be assessed
N0	No regional lymph node metastasis
N1	Metastasis in 1 to 3 regional lymph nodes
N2	Metastasis in 4 or more regional lymph nodes

Note: A tumour nodule in the pericolorectal adipose tissue of a primary carcinoma without histologic evidence of residual lymph node in the nodule is classified in the pN category as a regional lymph node. If the nodule has an irregular contour, it should be classified in the T category and also coded as V1(microscopic venous invasion) or as V2 (if it was grossly evident), because there is a strong likelihood that it represents venous invasion.

Distant Metastasis (M)

Mx	Distant metastasis cannot be assessed
M0	No distant metastasis
M1	Distant metastasis

APPENDIX 1(Continued)

TNM AND DUKES STAGING FOR COLORECTAL CANCER

Stage grouping

T	N	M	TNM	Dukes
Tis	N0	M0	0	-
T1	N0	M0	I	A
T2	N0	M0	I	A
T3	N0	M0	IIA	B
T4	N0	M0	IIB	B
T1-T2	N1	M0	IIIA	C
T3-T4	N1	M0	IIIB	C
Any T	N2	M0	IIIC	C
Any T	Any N	M1	IV	-

Adapted from:
AJCC Cancer Staging Manual. Sixth Edition. Springer 2002.

Criteria for high risk Dukes B (any of the following)

- High grade (3 or 4) tumours
- Lymphatic invasion
- Vascular invasion
- Less than 12 lymph nodes examined
- Bowel obstruction
- Perforation
- T4 tumour
- Elevated CEA

APPENDIX 2 – ECOG PERFORMANCE STATUS

ECOG PERFORMANCE STATUS*

Grade	ECOG
0	Fully active, able to carry on all pre-disease performance without restriction
1	Restricted in physically strenuous activity but ambulatory and able to carry out work of a light or sedentary nature, e.g. light house work, office work
2	Ambulatory and capable of all self care but unable to carry out any work activities. Up and about more than 50% of waking hours
3	Capable of only limited self care, confined to bed or chair more than 50% of waking hours
4	Completely disabled. Cannot carry on any self care. Totally confined to bed or chair
5	Dead

* As published in Am. J. Clin. Oncol.:

APPENDIX 3 – STUDY VISIT SCHEDULES & ASSESSMENTS

Assessments	Screening*		Baseline	Follow-up month (+/- 1 month)			Follow-up month (+/- 1 month) After Recurrence	Follow-up month (+/- 1 month) After Early Study Drug Discontinuation and no recurrence	Post Month 60
				3, 9, 15, 21, 27, 33	6,12, 18, 24, 30, 36	42, 48, 54, 60			
Written informed consent		x							
Demography, Tumour history, Medical history & family history			x						
Record surgical measurements,(For rectal cancer only)			x						
Adjuvant Therapy			x						
Vital signs (Body weight, BP, height), ECOG			x						
Hb	(Within 8 weeks prior to randomisation)		x		x				
Platelet count, Creatinine, Serum Bilirubin, AST, ALT	(Within 8 weeks prior to randomisation)	x							
CEA			x	x	x	x		x	
Imaging of abdomen (CT or CT colonogram or MRI or PET or Ultrasound)	To be done if not done within 16 months prior to randomization	x		x (Mth 6, 18 and 30) Optional; or frequency according to institutional practice					
Radiological examination of the Chest (including but not restricted to Chest x ray, CT thorax or PET scan)	To be done if not done within 16 months prior to randomization	x							
Colonoscopy/CT colonogram	Full colonoscopy if not done within 16 months prior to randomization	x		x (Mth 6, 18 and 30) Optional; or frequency according to institutional practice					
AE and SAE				x	x				
Death				x	x	x	x	x	x
Medical Events				x	x	x	x	x	x
Concomitant NSAIDs				x	x	x	x	x	x
Concomitant treatment/medication				x	x				
Recurrence, Salvage Chemotherapy				x	x	x	x	x	x

Notes:

* Screening can start after last dose of standard therapy

APPENDIX 4 – STUDY DRUG LABEL

Study code :ICR02/ASCOLT

Date of Dispensing

Subject No:

Subject Initial

Kit No:

Pack Batch No:

Expiry date

2 bottles x 100 tablets Aspirin/Placebo 100mg

For Oral Use Only

Take as directed/

Do not store above 25°C

FOR CLINICAL TRIAL USE ONLY

KEEP OUT OF REACH OF CHILDREN

Manufactured by Bayer Pharma AG D-51368

Leverkusen, Germany

1 INTRODUCTION

Colorectal cancer is the third most common cancer worldwide with almost 1 million new cases diagnosed each year. It is now also the third leading cause of cancer mortality in men and women with more than half of diagnosed patients dying from the disease. Mortality rates in Asian countries have risen concomitantly and in Singapore rates have doubled over the same period, with incidence rates amongst the highest in Asia. Colon cancer has recently surpassed lung cancer as the commonest cancer diagnosed in Singapore.

The utility of Aspirin and NSAIDs in preventing cancer, especially colon cancer is the subject of intense pre-clinical and clinical interest and investigation. Whereas high quality evidence (randomised controlled studies) indicates that Aspirin is effective in reducing colorectal adenomatous polyps; and numerous studies point towards an ability to prevent colorectal cancer; the role of Aspirin as an adjuvant agent in patients with established cancers remains to be defined. A nested cohort study (NURSES Health Study) suggested that the initiation of Aspirin after the diagnosis of colon cancer was able to reduce colorectal cancer specific mortality (HR 0.53, CI 0.33-0.86). Further, a pre-planned analysis of patients in the CALGB 89810 adjuvant Irinotecan trial suggested that patients who used Aspirin or a Cox-2 inhibitor regularly had half the risk of recurrence and death. Although this data is supportive of Aspirin's biological activity in this disease and possible role in adjuvant therapy, it needs to be confirmed in a randomised prospective trial. Two large randomised Cox-2 inhibitor studies had been undertaken to answer the same question, but were suspended prematurely, due to concerns of cardiovascular toxicity. In contrast, Aspirin is cardio-protective and is one of the most widely used drugs with a well-established safety profile.

We hypothesise through this randomised, placebo-controlled adjuvant study, that Aspirin in patients with Dukes C or high risk Dukes B colorectal cancer (ASCOLT) can improve survival in this patient population over placebo control. If indeed found to be beneficial, Aspirin will positively impact the lives of many individuals in Asia and the whole world as it is cheap and easy to administer.

2 STUDY OBJECTIVES

Primary objective

Null hypothesis: Among subjects with Dukes C or high risk Dukes B colorectal cancer, Disease Free Survival (DFS) between those randomised to Aspirin and those randomised to placebo control is equal.

Alternative hypothesis: Among subjects with Dukes C or high risk Dukes B colorectal cancer, DFS between those randomised to Aspirin and those randomised to placebo is not equal.

Primary objective: To compare DFS between the group randomised to Aspirin with the group randomised to placebo control in subjects with Dukes C or high risk Dukes B colorectal cancer.

Secondary objectives

1. To compare the DFS between the group randomised to Aspirin with the group randomised to placebo control in subjects with high risk Dukes B and Dukes C colon cancer.
2. To compare the overall survival (OS) between the group randomised to Aspirin with the group randomised to placebo control in subjects with Dukes C or high risk Dukes B colorectal cancer.

Exploratory objectives

1. To compare the DFS and OS between the group randomised to Aspirin with the group randomised to placebo control in subjects with Dukes C or high risk Dukes B colorectal within the following subgroups:
 - a. Baseline variables
 - i. Country.

Countries with small sample size (less than 25) will be pooled under 'Others' or with countries with similar ethnic population.

- ii. Resected high risk Dukes B colon cancer, Dukes C colon cancer, colon cancer and rectal cancer.
- iii. Exposed to Oxaliplatin, not exposed to Oxaliplatin.
- iv. Ethnicity (East Asian, South Asian, Caucasian and Others).
- v. Type of surgery (laparoscopic surgery, open surgery).
- vi. Chemotherapy duration (<3 months, 3-6 months, >6 months).
- vii. Age group (<70, ≥70).

b. Translational variables

- i. Compliant subjects, non-compliant subjects.

Compliant subject is defined as an individual who is on the study drug for at least 70% of days in first year from randomisation or up to treatment discontinuation or recurrence, whichever is earlier.

- ii. Duration of exposure to study drug (<1 year, 1-2 years, >2 years).

The duration of exposure to study drug during the treatment period is defined as the number of days from the first dose to the last dose excluding days of interruptions, i.e. "duration of exposure" = "last dosing date" – "first dosing date" – "days off medication" + "1 day".

- iii. PIK3CA mutations (mutant PIK3CA, wild-type PIK3CA)
- iv. COX-2 expression (positive for COX-2 overexpression, negative for COX-2 overexpression)

2. To compare the recurrence free survival between the group randomised to Aspirin with the group randomised to placebo control in subjects with Dukes C or high risk Dukes B colorectal cancer, taking into account competing risks of death due to other cancers and death due to other causes.

Subgroup analyses on PIK3CA mutations and COX-2 are restricted to subjects from Australia, New Zealand, Taiwan (Shuang Ho Hospital), Singapore (National Cancer Centre)

and Malaysia (University Malaya Medical Centre) sites who consented to tumour sample collection.

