1 TRIAL DESIGN

1.1 Study Population

The study population consists of Dukes C colon cancer, high risk Dukes B colon cancer, Dukes B rectal cancer or Dukes C rectal cancer subjects who have completed the resection of primary tumour. The population will be treated with standard therapy (chemotherapy ± radiotherapy). During the last cycle of standard therapy, patients would be invited to

participate in this study. Once informed consent is taken and within 120 days of completion of the standard therapy, they would be checked for trial eligibility.

Inclusion Criteria

- Male or female outpatient of ≥ 18 years of age or \geq country's legal age for adult consent
- Dukes C colon cancer, high risk Dukes B colon cancer, Dukes B rectal cancer or Dukes C rectal cancer
- Undergone complete resection of primary tumour
- Completed standard therapy (at least 3 months of chemotherapy \pm radiotherapy)
- Within 120 days of completion of standard therapy (surgery, chemotherapy \pm radiotherapy)
- Eastern Cooperative Oncology Group (ECOG) performance status 0 to 2
- Satisfactory haematological or biochemical functions (tests should be carried out within 8 weeks prior to randomisation): Results of clinical investigations carried out within 8 weeks prior to randomisation can be used in place of the required screening investigations. Patients with mild laboratory abnormalities can be included at the discretion by the site principal investigator, and after approval by ASCOLT Trial Management Group
 - ANC $\geq 1.0 \times 10^9/L$
 - Platelets $\geq 100 \times 10^9/L$
 - Creatinine clearance ≥ 30 mL/min
 - Total bilirubin ≤ 2.0 x the upper limit normal
 - AST & ALT ≤ 5 x the upper limit normal

Completed the following investigations

- Colonoscopy (or CT colonogram (within 16 months prior to randomization))
- Imaging of abdomen (CT or CT colonogram or MRI or PET or Ultrasound) within 16 months prior to randomization
- Written informed consent

Exclusion Criteria

- Pre-existing familial adenomatous polyposis, inflammatory bowel disease or ulcerative colitis
- Active gastritis or active peptic ulcer
- History of continuous daily use of proton pump inhibitor (PPI) more than 1 year prior to consent
- Gastrointestinal bleeding within the past one year
- Haemorrhagic diathesis (i.e. haemophilia)
- Uncontrolled hypertension (untreated systolic blood pressure > 160 mmHg, or diastolic blood pressure > 95 mmHg)

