4.6 Time-to-event Endpoints

For primary outcome of DFS, survival curves will be constructed using the Kaplan-Meier method. Product-limit estimates of 3- and 5-year survival rates will be calculated. Median survival times will also be reported. The complementary log-log transformation will be used for deriving the median survival times corresponding 95% CIs. The primary analysis will be a mITT analysis which uses stratified logrank test adjusting for trial stratification factor

(centre pooled by country (categorical), type of tumour (Dukes C colon vs. high risk Dukes B colon vs. rectal; categorical) and type of adjuvant chemotherapy (exposed vs. not exposed to Oxaliplatin; categorical)) to generate p-value comparing the treatment groups, followed by multivariate Cox proportional hazard (PH) regression model to estimate adjusted HR and its corresponding 95% CI. The multivariate Cox PH regression model will also include the trial stratification factors used in the stratified logrank test as covariates. Additional covariates such as time from surgery to first chemotherapy in days (continuous), type of surgery (laparoscopic surgery vs. open surgery; categorical), chemotherapy duration (<3 months vs. 3-6 months vs. >6 months; categorical) and age group (<70 vs. ≥ 70 years old; categorical) will be added as part of sensitivity analysis. The CI of the HR will be based on profile-likelihood. Firth's correction may be used if monotone likelihood phenomenon is observed. Unadjusted HR and p-value from non-stratified logrank test will also be reported as supplementary results.

As part of secondary objective, the same analysis on DFS will be repeated for sub-population of colon cancer except that the covariate, type of tumour, will consist of only two categories: Dukes C colon vs. high risk Dukes B colon.

The secondary outcome of OS will be analysed in a similar manner as the primary endpoint, except that repeated analysis on colon cancer sub-population will not be done.

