For all subgroup analyses of DFS and OS by different countries, tumour types (high risk Dukes B colon, Dukes C colon, colon, rectal), adjuvant chemotherapy types (exposed to Oxaplatin, not exposed to Oxaliplatin), ethnic groups (East Asian, South Asian, Caucasian, Others), type of surgery (laparoscopic surgery, open surgery), chemotherapy duration (<3 months, 3-6 months, >6 months), age group (<70, ≥ 70), levels of compliance (<70%, $\geq 70\%$), duration of exposure to drug (<1 year, 1-2 years, >2 years), PIK3CA mutations (mutant PIK3CA, wild-type PIK3CA) and COX-2 expression (positive for COX-2 overexpression, negative for COX-2 overexpression), tests for interactions between treatment group and the subgroup variable of interest will be conducted first. As the subgroups under tumour types are not mutually exclusive, the test for interaction will be based on the original mutually

exclusive groups. Results of subgroup analyses will be presented in forest plots. Subgroup analyses will be considered as exploratory.

Appropriateness of Cox PH regression model will be checked using graphical method of log-log survival curves for treatment indicator and each covariate. Continuous covariate will be dichotomised at mean value to check for the PH assumption. PH assumption will be considered not satisfied if there is strong evidence of non-parallelism in the log-log survival curves. Should there be at least one covariate not satisfying the PH assumption, “no-interaction” (i.e. estimated coefficients not varying by stratum) stratified Cox regression model will be used instead. The model will be stratified by strata formed after combining categories of all covariates which did not satisfy the PH assumption. Covariate(s) which satisfies the PH assumption will remain included in the stratified model. If the treatment indicator is found to not satisfy the PH assumption, time-varying HR will be obtained by partitioning the follow-up time into 1-year intervals.

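### The exploratory treatment-by-age interaction is tested only with age cut at 70, although age in years is collected; under plausible assumptions this loses much of the power to see a gradual age trend (low severity)

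*SAP*

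**What the plan says.** Section 2 of the SAP (Exploratory objectives, item 1.a.vii) lists the age subgroup as "Age group (<70, ≥70", closing the bracket there. No other form of age is defined for the subgroup analyses.

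Section 4.6 repeats this split among the DFS and OS subgroup variables and says that "tests for interactions between treatment group and the subgroup variable of interest will be conducted first". Since the subgroup variable has two levels, the planned age interaction is a two-group comparison. The same section states: "Subgroup analyses will be considered as exploratory".

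Section 4.6 also uses the split in the extended Cox model, where "age group (<70 vs. ≥ 70 years old; categorical) will be added as part of sensitivity analysis". That model keeps another covariate on its original scale: "time from surgery to first chemotherapy in days (continuous").

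The Table 1 shell in SAP Appendix 1 summarises age in years by mean, SD, median, IQR and range, so exact age is held. The entry criterion is "Male or female outpatient of ≥ 18 years of age" (or the country's legal age for consent), with no upper limit. Neither document explains the choice of 70 or plans an analysis of age in years.

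**The concern.** A cut at 70 treats everyone from 18 to 69 as the same age, and likewise everyone from 70 upwards. If aspirin's net effect changes gradually with age, the test ignores all variation in age within the two groups. It is weakest when few patients are 70 or over.

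DFS and OS both count death from any cause, so age is a natural candidate to modify the effect, and readers will look at this row of the forest plot. A non-significant result from an underpowered two-group test can easily be read as evidence that age does not matter. What is at stake is how informative one exploratory result is for each endpoint. The main conclusion of the trial does not depend on it.

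**Working it through.** **1. The plan's own figure.** SAP section 3.5 gives 300 events for HR 0.72, two-sided 5%, 80% power, 1:1 allocation. With z-values 1.96 + 0.84 = 2.80:

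- Schoenfeld: 4 × 2.80² / (ln 0.72)² = 291 events.
- Freedman: (1.72/0.28)² × 2.80² = 297 events.
- Events expected from 1587 subjects, 10% attrition and 79% pooled 5-year DFS: 1587 × 0.90 × 0.21 = 299.9.

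The 300 is reproduced. It concerns the main effect. The documents give no power for any interaction.

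**2. Assumptions for the age test.** The documents do not give the mean, the SD or the share aged 70 or over. I assume roughly normal ages with mean 55-65 and SD 10-12, and a treatment log hazard ratio that is linear in age.

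**3. Information kept by the cut.** With z = (70 − mean)/SD, p = P(age ≥ 70) and φ the standard normal density, the two-group variable keeps this share of the information on a linear trend:

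kept = φ(z)² / [p(1 − p)]

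If the test in years has 80% power, the test with the cut has power Φ(2.80 × √kept − 1.96).

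| Mean / SD | z | p (≥70) | φ(z) | Kept | Power with cut |
|---|---|---|---|---|---|
| 55 / 10 | 1.50 | 7% | 0.1295 | 27% | 31% |
| 55 / 11 | 1.36 | 9% | 0.1574 | 31% | 35% |
| 60 / 11 | 0.91 | 18% | 0.2639 | 47% | 48% |
| 65 / 10 | 0.50 | 31% | 0.3521 | 58% | 57% |
| 65 / 12 | 0.42 | 34% | 0.3658 | 60% | 58% |

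The first and last rows are the extremes of the assumed grid. Worked for the first: 0.1295² / (0.0668 × 0.9332) = 0.269, and Φ(2.80 × 0.519 − 1.96) = 0.31.

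**4. How far this depends on normality.** Under normality the best case is a median split, which keeps 64% (a loss of 36%). Two uniform and three left-skewed age distributions gave losses of 44-67%. A simulated Cox interaction test (1587 subjects, about 287 events, log hazard ratio changing 0.33 per SD of age, 300 runs each) gave:

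| Mean / SD | Share ≥70 | Power, years | Power, cut | Information kept |
|---|---|---|---|---|
| 58 / 11 | 14% | 81% | 52% | 47% |
| 60 / 10 | 16% | 77% | 49% | 49% |
| 64 / 11 | 29% | 81% | 59% | 58% |

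For the same three settings the formula keeps 41%, 44% and 57%. The simulated losses are therefore slightly smaller, but of the same order.

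**5. How large an interaction this is.** With 300 events, 80% power in years needs a slope of 2.80/√(300/4) = 0.32 per SD of age, a ratio of hazard ratios of 1.38 per SD. The whole assumed treatment effect is ln 0.72 = −0.33. At half that slope, power in years is Φ(1.40 − 1.96) = 29%. With the cut it is Φ(1.40 × √0.269 − 1.96) = 11% to Φ(1.40 × √0.598 − 1.96) = 19%.

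**6. The sensitivity Cox model.** A simulation with 1587 subjects, about 168 deaths, mean age 60, SD 11, a strong prognostic age effect (log hazard ratio 0.4 per 10 years) and a true HR of 0.72 (150 runs) gave a mean treatment HR of 0.712 with no age term, 0.711 with the cut and 0.711 with age in years. The standard error was 0.157 in all three.

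**The case against.** The strongest reply is that no decision depends on this test. The SAP calls the subgroup analyses exploratory, and age is one of 11 subgroup variables. Age is absent from the primary stratified logrank test and from the primary Cox model. The cut is fixed in advance, so there is no data-driven choice of threshold. All of this stands, and it is why the severity is low.

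A second reply is that the interaction in the power comparison is very large and that, at half its size, power is poor with either form of age. This also stands: age in years improves the test but does not make it well powered. It does not justify giving up information that is already held.

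A third is that a two-group test is more powerful if the effect truly steps at 70. That is correct, but the SAP gives no reason to expect such a step.

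A reader might go further and infer three things that the documents do not support:

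- *That a fixed, known share of the information is lost.* There is no age distribution in either document. The percentages follow from the assumed distribution and from linearity.
- *That the age-adjusted sensitivity estimates are compromised*, because age enters only as "age group (<70 vs. ≥ 70 years old; categorical"). Randomisation balances age on average, and step 6 shows almost no change in the treatment HR or its standard error. That model is in any case a sensitivity analysis.
- *That the primary result or sample size is affected.* Neither uses age.

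**Conclusion.** The point holds for the interaction test. The SAP plans to examine effect modification by age only through a cut at 70, while exact age is collected. If ages are roughly normal with mean 55-65 and SD 10-12, and the effect changes linearly with age, the cut keeps about 27-60% of the information. An interaction with 80% power in years would have about 31-58% power. The loss is larger if fewer than about 7% of patients are 70 or over, and there is none if the effect steps exactly at 70.

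Severity is low: the analysis is exploratory, and the primary DFS analysis, the 300 events and the 1587 subjects do not change. Whichever form of age is used, a non-significant interaction should not be reported as evidence that the effect is the same at all ages.

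**What to change.** In SAP section 4.6, state that the treatment-by-age interaction for DFS and for OS will be tested with age in years, as one pre-specified linear term. Add a restricted cubic spline as a descriptive check, without a further significance test. Keep the under-70 and 70-and-over rows in the forest plots for display, and note there that the interaction p-value comes from age in years.

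This takes a short SAP edit and a changed model term for one exploratory test, with no new data. The price is lower power should the effect step exactly at 70.

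Using age in years in the sensitivity Cox model is optional, since it barely changes the result. It would also touch other rules. Section 4.6 dichotomises continuous covariates at the mean to check proportional hazards. Table 7, footnote 3, takes its p-value from a logrank test stratified by the model's covariates, and age in years cannot serve as a stratum. The continuous time-from-surgery term already raises that second difficulty.
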